6.5.1.2. Oral Bridging- Standard of Care Antiretroviral Therapy (SOC ART)

For patient participants who are unable to attend an IM injection visit nor obtain oral CAB + RPV from the site, oral bridging with any commercially available, guideline-recommended, SOC ART regimen is permitted. The start date of oral bridging should be within the dosing window for the missed IM dosing visit. Sites must contact the study medical monitor for approval of SOC ART as oral bridging, confirm IM restart

instructions, and to ensure the participant remains appropriate for resumption of IM dosing.

It is important to collect relevant clinical information, including adverse events, from the participant through alternative means, e.g. by telephone contact.

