7.1.3. Strategy for Intercurrent (Post-Randomization) Events

Participants with last available HIV-1 RNA measurement less than 50 copies/mL while the participant is on treatment within the analysis visit window of interest are classified as HIV-1 RNA < 50 c/mL. Participants without evaluable HIV-RNA data for the visit of interest or who change treatment not permitted per protocol before the analysis window are considered non-responders.

Participants with last available HIV-1 RNA measurement greater or equal to 50 copies/mL while the participant is on treatment within the analysis visit window of interest are classified as HIV-1 RNA \geq 50 c/mL. Participants without evaluable HIV-RNA data for the visit of interest and who discontinue treatment for reasons not related to adverse event while having HIV-1 RNA \geq 50 copies/mL at time of discontinuation or who change study treatment not permitted per protocol before the analysis window are also classified as having HIV-RNA \geq 50 copies/mL.

Missing viral load values for reasons related to COVID-19 issues (e.g. participant is unable to have viral load assessed due to barriers in attending the clinic during the pandemic or COVID-19 related adverse events leading to treatment discontinuation) will

be considered as random missingness and classified the same as all other missingness for the primary efficacy Snapshot analysis. A sensitivity analysis using a modified Snapshot which includes subcategories for Covid-19 related and Non-Covid-19 related missingness will also be performed to display the impact of Covid-19 intercurrent events on the study. See [Appendix 8](#) for Modified Snapshot Algorithm details.

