13.8. Appendix 8: Snapshot Algorithm Details

Detailed Algorithm Steps

 • Consider an analysis visit window for Month X as defined in Table 2. • The HIV-1 RNA threshold of 50 will be analysed in this study • The COVID-19 pandemic presents significant logistical challenges for many clinical sites around the world, with variable restrictions being placed on site resources and operations, and on an individual participants ability to attend clinic visits. The snapshot algorithm is modified to allow for the presentation of full scope of COVID-19 relatedness. The analysis window for 'Month 12' and HIV-1 RNA threshold of '50 c/mL' are used for the purpose of illustration. A participant's Snapshot response and reason at Month 12 are categorized as below. 
 ○ HIV-1 RNA < 50 c/mL ○ HIV-1 RNA ≥ 50 c/mL 
 Data in window not below 50 
 Non-COVID-19 related 
 Discontinued for lack of efficacy Discontinued for other reason while not below 50 COVID-19 related 
 Discontinued for lack of efficacy Discontinued for other reason while not below 50 ○ No Virologic Data at Month 12 Window 
 Non-COVID-19 related 
 Discontinued study due to AE or death Discontinued study for other reasons On study but missing data in window COVID-19 related 
 Discontinued study due to AE or death Discontinued study for other reasons On study but missing data in window Change in background therapy* 
* Note: Use of CAB + RPV oral bridging and SOC oral bridging medication, where the latter is due to unavailability of CAB/RPV IM injections or oral CAB+RPV during the pandemic, will not be considered a "Change in background therapy" in the Snapshot algorithm. All other permanent changes in ART are not permitted in this protocol.

Detailed steps
 
 • Please note that the following scenarios will NOT be penalized in the Snapshot algorithm Oral bridging (CAB+RPV or SOC, where SOC oral bridging medication is permitted during COVID-19 pandemic due to the unavailability of the CAB/RPV IM injections and oral CAB+RPV)

Detailed Algorithm Steps		
Condition ('Month 12' indicates Month 12 window)	Response	Reasons

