1. If non-permitted change in background therapy prior to Month 12	HIV-1 RNA \geq 50	Change in background therapy
2. If non-permitted change in background therapy during Month 12		

 Last on-treatment VL during Month 12 prior to/on the date of change \geq 50 c/mL 	HIV-1 RNA \geq 50	Data in window not below 50

 Last on-treatment VL during Month 12 prior to/on the date of change $<$ 50 c/mL 	HIV-1 RNA $<$ 50	

 No VL during Month 12 prior to/on the date of change 	HIV-1 RNA \geq 50	Change in background therapy
3. If none of the above conditions met		
3.1. On-treatment VL available during Month 12		

 Last on-treatment VL during Month 12 \geq 50 c/mL 	HIV-1 RNA \geq 50	Data in window not below 50

 Last on-treatment VL during Month 12 $<$ 50 c/mL 	HIV-1 RNA $<$ 50	
3.2. No on-treatment VL during Month 12		
3.2.1. If participants are still on study, i.e. a participant has not permanently discontinued the study treatment yet, or if a participant permanently discontinued the study treatment and the upper bound of analysis snapshot window is prior to the following date: 
 Min[max(Date of last injection + 35, Date of Last Dose of Oral Study Treatment (CAB+RPV, SOC Bridging) + 1), LTFU ART Start Date] 		
3.2.1.1. If no on-treatment VL during Month 12 is not due to COVID-19	No virologic data at Month 12 Window	On study but missing data in window (Non-COVID-19 related)
3.2.1.2. If no on-treatment VL during Month 12 is due to COVID-19	No virologic data at Month 12 Window	On study but missing data in window (COVID-19 related)

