	PHYSICIAN DECISION	xx (xx.x%)	xx (xx.x%)	xx (xx.x%)
	WITHDRAWAL BY SUBJECT	xx (xx.x%)	xx (xx.x%)	xx (xx.x%)
	COVID-19 RELATED	x (xx.x%)	x (xx.x%)	x (xx.x%)
	FREQUENCY OF INJECTIONS	x (xx.x%)	x (xx.x%)	x (xx.x%)
Long-term Follow-up Phase	LOST TO FOLLOW-UP			xx (xx.x%)
	WITHDRAWAL BY SUBJECT			xx (xx.x%)
	SUBJECT RELOCATED			x (xx.x%)

CONFIDENTIAL

213199

BURDEN OF PROCEDURES

x (xx.x%)

[1] Subjects may have only one primary reason.

[2] Percentages for subreasons may sum to more or less than 100%. Subjects may have more than one subreason underneath a single primary reason. Subjects are not required to indicate subreasons.

Intervention/Extension phase: status and reason for withdrawal based on date and reason collected in the study treatment discontinuation form. Long term Follow-up: completion/withdrawal based on data collected in the Study Conclusion form.

Protocol: 213199
 Population: Safety

Page 1 of 1

Table EFF_T1
 Summary of Study Outcomes (50 c/mL cutoff) at Month 12 (Intervention Phase)
 - Snapshot Analysis

Outcome	Q4W IM (N=xx)
HIV-1 RNA<50 c/mL	xx (xx%)
HIV-1 RNA>=50 c/mL	xx (xx%)
Data in window not below threshold	xx (xx%)
Discontinued for lack of efficacy	xx (xx%)
Discontinued for other reason while not below threshold	xx (xx%)
Change in ART [1]	xx (xx%)
No Virologic Data	xx (xx%)
Discontinued study due to AE or Death	xx (xx%)
Discontinued study for Other Reasons	xx (xx%)
On study but missing data in window	xx (xx%)

[1] Excludes CAB + RPV Oral Bridging and COVID-19 related temporary oral bridging with SOC.

Protocol: mid213199
 Population: Safety

Page 1 of 1

Table EFF_T2
 Summary of Study Outcomes (50 c/mL cutoff) at Month 12 (Intervention Phase)
 - Snapshot Analysis

Outcome	Q4W IM (N=xx)
HIV-1 RNA<50 c/mL	xx (xx%)
HIV-1 RNA≥50 c/mL	xx (xx%)
Data in window not below threshold	xx (xx%)
Non-COVID-19 related	xx (xx%)
Discontinued for lack of efficacy	xx (xx%)
Discontinued for other reason while not below threshold	xx (xx%)
COVID-19 related	xx (xx%)
Discontinued for lack of efficacy	xx (xx%)
Discontinued for other reason while not below threshold	xx (xx%)
Change in ART [1]	xx (xx%)
No Virologic Data	xx (xx%)
Non-COVID-19 related	xx (xx%)
Discontinued study due to AE or Death	xx (xx%)
Discontinued study for Other Reasons	xx (xx%)
On study but missing data in window	xx (xx%)
COVID-19 related	xx (xx%)
Discontinued study due to AE or Death	xx (xx%)
Discontinued study for Other Reasons	xx (xx%)
On study but missing data in window	xx (xx%)

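### The SAP spares SOC oral bridging from the Snapshot change-in-therapy category only when it is COVID-19 related, although the protocol permits it without that condition, so permitted bridging could be scored HIV-1 RNA ≥50 c/mL

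*SAP*

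**What the plan says.** **Protocol.** Section 6.5.1.2 covers a participant who can neither attend an injection visit nor get oral CAB+RPV from the site. For that case, "oral bridging with any commercially available, guideline-recommended, SOC ART regimen is permitted". A further condition is attached: "Sites must contact the study medical monitor for approval of SOC ART as oral bridging". COVID-19 is not mentioned. Pandemic bridging is handled separately in Section 6.5.2 and Appendix 14, and Appendix 14 states that it does not apply to management issues unrelated to COVID-19.

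**SAP, exemption wording.** Four places name the bridging that is not counted as a change of therapy:

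- Appendix 8, note under the outcome categories: CAB+RPV bridging is exempt outright, and SOC bridging "where the latter is due to unavailability of CAB/RPV IM injections or oral CAB+RPV during the pandemic".
- Appendix 8, list of scenarios that are not penalised: CAB+RPV or SOC bridging, "where SOC oral bridging medication is permitted during COVID-19 pandemic due to the unavailability of the CAB/RPV IM injections and oral CAB+RPV".
- Appendix 13, footnotes to EFF_T1 and EFF_T2 (the same text in both): "Excludes CAB + RPV Oral Bridging and COVID-19 related temporary oral bridging with SOC".

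**SAP, penalty wording.** Step 1 of the algorithm is triggered as follows: "If non-permitted change in background therapy prior to Month 12". Section 7.1.3 applies the same limit, since participants "who change study treatment not permitted per protocol before the analysis window are also classified as having HIV-RNA" at or above 50 c/mL.

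**SAP, treatment definitions.** Section 13.5.1 counts SOC bridging as study treatment, and Table 11 counts it toward on-treatment time. Neither carries a COVID-19 restriction.

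**The concern.** The protocol's permission and the SAP's exemption do not cover the same participants. Someone who bridges with SOC ART for a reason unrelated to COVID-19, within the terms of 6.5.1.2, has followed the protocol but falls outside the exemption in the shell footnotes. The footnotes would place that person under the change-in-ART row, which sits within HIV-1 RNA ≥50 c/mL.

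Step 1 is applied before any viral load is consulted. A participant who bridged before the window, returned to injections and was below 50 c/mL at Month 12 would therefore be reported as not suppressed. That defeats the virology-first hierarchy set out in SAP 13.5.3. It would lower the suppressed proportion and raise the ≥50 c/mL proportion for a non-virologic reason, in the Month 12 Snapshot tables (2.1 to 2.6), including those by country and implementation arm.

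**Working it through.** The plan gives no figure to reproduce here. The check is a comparison of texts followed by simple arithmetic on size.

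**1. Is the protocol permission general?** Yes, within its conditions. Section 6.5.1.2 requires that the participant can neither attend nor obtain oral CAB+RPV, and that the medical monitor approves. Because Appendix 14 is confined to COVID-19 impact, 6.5.1.2 stands as an independent permission.

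**2. Is the SAP exemption narrower?** Yes. CAB+RPV bridging is spared without condition, whereas SOC bridging is spared only with a pandemic qualifier (Appendix 8) or a COVID-19 qualifier (footnotes).

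**3. What happens to one permitted, non-COVID SOC bridge under each text?** Assume the participant is suppressed throughout.

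- Steps 1 and 2 and Section 7.1.3, with permission read from the protocol: the change is permitted, there is no penalty, and the last on-treatment viral load in the window gives <50 c/mL.
- EFF_T1/EFF_T2 footnotes, bridge before the Month 12 window: not exempt, so step 1 gives ≥50 c/mL.
- Footnotes, bridge inside the window (Month 12 target day −42 to +42) after a viral load <50 c/mL in that window: step 2 uses that value and gives <50 c/mL.
- Footnotes, bridge inside the window with no earlier viral load in it: step 2 gives ≥50 c/mL.
- Appendix 8 notes: the result depends on whether the pandemic wording is read as a period of time or as a cause.

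The same participant can thus be classified in two ways from one SAP.

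**4. Size per case.** Shift = 1/N for each reclassified participant, down in the <50 c/mL proportion and up in the ≥50 c/mL proportion. The planned numbers in SAP 2.4.1 are 450 evaluable and 474 enrolled.

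- N = 450: 1/450 = 0.22 percentage points.
- N = 474: 1/474 = 0.21 percentage points.

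**5. Illustration.** The number of reclassified cases k is an assumption, because the documents give no frequency. The intervals are exact Clopper-Pearson 95%, the method named in SAP 7.1.4.1. With N = 450 and nobody else at ≥50 c/mL:

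- k = 1: 1/450 = 0.22% (0.01 to 1.23)
- k = 2: 2/450 = 0.44% (0.05 to 1.60)
- k = 5: 5/450 = 1.11% (0.36 to 2.57)
- k = 10: 10/450 = 2.22% (1.07 to 4.05)

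If 5 of 450 were ≥50 c/mL for other reasons (also assumed), five reclassifications would take the proportion from 5/450 = 1.11% to 10/450 = 2.22%.

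**The case against.** The strongest reply is that the operative rule already gives the right answer. Steps 1 and 2, Section 7.1.3 and the FDA example in Appendix 8 all confine the penalty to changes that the protocol does not permit, and 6.5.1.2 permits SOC bridging. Appendix 8 also closes its note with "All other permanent changes in ART are not permitted in this protocol", and bridging is temporary. Its pandemic wording may describe a period rather than a cause. The footnotes sit in example shells that are visibly not fully adapted: the column heading is Q4W in a study that doses every two months. Any misclassification would also be traceable, because the change-in-ART row is separate and Listing 31 flags SOC bridging.

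Much of this stands. A reader might infer that permitted SOC bridging will certainly be scored as failure; the documents do not support that, because the penalty wording points the other way. A reader might also infer that the protocol allows SOC bridging for any reason; it does not, given the conditions in 6.5.1.2.

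The reply does not remove the problem. The only SAP text that names which bridging is spared carries the pandemic or COVID-19 limit all four times, and the second Appendix 8 note describes the permission itself in pandemic terms. A programmer who looks up what counts as permitted in Appendix 8 and the shells would reasonably code the narrower rule. Traceability helps someone find the error afterwards but does not settle which classification was pre-specified.

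**Conclusion.** The SAP is internally inconsistent, and its stated exemption is narrower than Protocol 6.5.1.2. Under the footnotes, and ambiguously under Appendix 8, permitted non-COVID SOC bridging before the Month 12 window, or inside it with no earlier in-window viral load, would be scored ≥50 c/mL despite suppression.

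Each case is worth 0.21 to 0.22 percentage points. The total effect cannot be stated, because the number of such participants is not given and may be zero. A few cases would matter mainly if the ≥50 c/mL proportion is otherwise small.

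The reach is limited. It would be tempting to call this a false virologic failure, but protocol-defined confirmed virologic failure rests on two successive viral loads of at least 200 c/mL and does not depend on the change-in-therapy rule. Snapshot is a secondary, descriptive endpoint here, and the primary endpoint, based on staff questionnaires and interviews, is untouched. The correction is still worth making, because the proportions should not depend on which page was programmed from.

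**What to change.** - Reword both Appendix 8 notes and the EFF_T1 and EFF_T2 footnotes so that all oral bridging permitted under Protocol 6.5.1 or Appendix 14, whether CAB+RPV or SOC and whether COVID-19 related or not, is exempt from the change-in-background-therapy category.
- Define a non-permitted change in Appendix 8 as any change of ART outside those provisions, so that steps 1 and 2 and Section 7.1.3 use one meaning.
- If the sponsor does intend to penalise non-COVID SOC bridging, say so explicitly, give the reason, and amend steps 1 and 2 and Section 7.1.3 to match.

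The cost is a wording change in four places, one definition and one program condition. The SOC bridging flag planned for Listing 31 can be used to identify these cases.

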HIV-1 infected participants who meet all eligibility criteria will be switched from their pre-baseline regimen to an oral regimen (CAB 30 mg + RPV 25 mg once daily) during the **oral lead-in phase**. Participants will return to the clinic, and if laboratory and clinical evaluations continue to support progression into the **injection treatment phase** of the study, will take the last dose of their oral regimen (CAB 30 mg + RPV 25 mg) and receive the first dose of CAB LA (600 mg) + RPV LA (900 mg) injections on the same day (Month 1). The participant will receive the second injections CAB LA (600 mg) + RPV LA (900 mg) one month later (Month 2). All subsequent injections will occur every two months thereafter (Month 4, Month 6, etc) for a total of 7 doses of CAB LA

and RPV LA (Table 7). The total length of the treatment phase is approximately one year.

Table 7 Dosing Regimen

Oral Lead-in to End of Study ⁺		
CAB + RPV Oral Lead-In		
Oral Lead-in (Day 1 to Month 1)	• Take one tablet of CAB 30 mg + RPV 25 mg once daily	
two once daily tablets taken with food		
CAB LA + RPV LA Injections		
Dose 1 (Month 1)	Receive last dose of oral CAB + RPV regimen	
	 Receive CAB LA 600 mg given as 1 X 3 mL IM injection 	
	 Receive RPV LA 900 mg given as 1 X 3 mL IM injection 	
Dose 2 to Dose 7 (Month 2- End of Study ⁺)	 Receive CAB LA 600 mg given as 1 X 3 mL IM injection 	
two 3 mL injections every two months	 Receive RPV LA 900 mg given as 1 X 3 mL IM injection 	
+Until after dose 7 (Month 12) when locally approved and commercially available, the participant no longer derives clinical benefit, the participant meets a protocol-defined reason for discontinuation or until development of CAB LA or RPV LA is terminated		

The dosing window for the second injections will be +0/-7 days from the projected target date (target date is established at Month 1). All subsequent injection windows (starting with Dose 3) will be +7/-7 days from the projected target date. Doses outside of the window *may* be allowed with prior Medical Monitor approval.

Participants will continue CAB LA + RPV LA until:

- After dose 7 and when the study intervention is locally approved and available for the Investigator to prescribe. Note if intervention is not locally approved at dose 7 they will continue into the Extension Phase (see Section 6.8).
- the participant no longer derives clinical benefit
- the participant meets a protocol-defined reason for discontinuation

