6.5.3. IM Dosing

Participants receiving CAB LA and/or RPV LA are anticipated to be at risk for development of virologic resistance if antiretroviral therapy is interrupted. The time period during which participants are at risk for development of virologic resistance may be determined by the period between when drug levels fall below therapeutic values and when they fall below levels which exert selective pressure on HIV. This time period will vary by ART agent and is dependent upon effective concentration, inhibitory concentration, and half-life. Plasma concentrations of both LA drugs may be measurable for more than one year following IM injections. Any interruption in IM dosing should be discussed with the Medical Monitor. Investigators should ensure that the participant initiates alternative highly active ART to minimize the risk of developing resistance as concentrations of and RPV decline over time.

CAB LA + RPV LA dosing for participants transitioning from oral CAB + RPV is as follows:

All injections should be planned as single injections per drug.

Target Date

The patient's 'target date' is determined by their first injection date and ideally is the same date for every injection. For example, if the1st dose (Month 1) is January 15th, then dose 2 (Month 2) will be February 15th, and dose 3 (Month 4) will be April 15th, etc.

Since the first injection visit (Month 1) will determine the future injection visit schedule for participants and ideally be between the 1st and 28th day of the month. Planning for the first injection visit date (within allowed visit windows) should take into consideration the availability of the participants to adhere to future visit windows (planned vacations, business trips, *etc.*).

Treatment Injections- Months 1 and 2 -one month apart

Participants will take the last dose of their oral (CAB 30 mg + RPV 25mg) and receive the first CAB LA (600mg) + RPV LA (900mg) injections (within 2 hours of the final oral dose of CAB + RPV).

The second dose (CAB LA 600mg + RPV LA 900mg) will be administered one month later (preferable on the same target date as Dose 1). The dosing window for Dose 2 allows administration -7days of the proposed visit date but not later.

Treatment Injections- Months 4- Q2M dosing

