analysis are those after first injection at Month 1. (. Each injection visit is counted only once. Individual CAB and RPV injections administered at the same visit are not counted twice. "Extra" unscheduled injections are excluded from all derivations. For example, if during a scheduled visit a participant receives 1 ml of injection instead of 2 ml due to a dosing error, but this participant returns one week later for the remaining 1 ml injection, then the additional visit is excluded. If a participant receives an extra injection at an unscheduled visit by mistake, this visit will also be excluded.

- The categories of Timeliness of Injections relative to Date of Projected Dosing Visits are listed below:
 - < -14 days
 - -14 to - 8 days
 - -7 to 1
 - 0
 - 1 to 7 days
 - 8 to 14 days
 - >14 days
 - Missed Injection without Oral Bridging (COVID-19 related)
 - Missed Injection without Oral Bridging (Non COVID-19 related)
 - Missed Injection with Oral Bridging (COVID-19 related)
 - Missed Injection with Oral Bridging (non COVID-19 related)
 - Missed Injection with subsequent SOC ART Initiation
- The following categories surrounding out of window (OOW) visits will also be calculated separately for participants at each visit.
 - Oral Bridging without a Missed Injection
 - OOW Injection with Oral Bridging (non-Covid-19 related)
 - OOW Injection with Oral Bridging (Covid-19 related)
 - OOW Injection without Oral Bridging (Covid-19 related)
- Injection visits are expected bi-monthly after an initial Month 1 Q4W injection from Month 2 until the nominal month of a participant's last injection visit during the phase(s) of interest. For example:
 - If a participant discontinues study treatment with last injection visit occurring at nominal visit Month 6, then injection visits are expected at Month 1, Month 2, Month 4, and Month 6.
- Expected injection visits will include all treatment visits (not LTFU) where an assessment was recorded regardless of whether the injection took place, including visits where treatment was discontinued.
- Missed injections with subsequent LTFU SOC ART Initiation are not counted in 'Missed Injection without Oral Bridging' categories. Missed injections will be slotted to this category if LTFU SOC ART is initiated within 30 days of the missed injection.
- Out of Window injections are determined based on criteria listed in protocol Section 4.3.3.
- Covid-19 relatedness is determined as follows:

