[1] Excludes CAB + RPV Oral Bridging and COVID-19 related temporary oral bridging with SOC.

Protocol: mid213199
 Population: Safety

Table SAF_T1

Summary of Adherence to CAB LA + RPV LA Dosing Schedule by Visit, Country, Site, and COVID Impacted/Non-Impacted (Intervention Phase)

Country: xxxxx {Programmer's Note: repeat for each of 5 countries overall, each individual site, and total}
 Site ID: xxxxx
 COVID-19: xxx {non-impacted + impacted/non-impacted/impacted}

Timeliness of Injections Relative to Date of Projected Dosing Visits	Month 2	Month 4	Month 6	Month 8	Month 10	Month 12	Total
No. of Expected Injection Visits	xxxx	xxxx	xxxx	xxxx	xxxx	xxxx	xxxx
<-14 days	xx (%)	xx (%)	xx (%)				
-14 days to - 8 days	xx (%)	xx (%)	xx (%)				
-7 days to - 1 days	xx (%)	xx (%)	xx (%)				
0	xx (%)	xx (%)	xx (%)				
1 days to 7 days	xx (%)	xx (%)	xx (%)				
8 days to 14 days	xx (%)	xx (%)	xx (%)				
> 14 days	xx (%)	xx (%)	xx (%)				
Missed Injection without OB (non-COVID-19 related)	xx (%)	xx (%)	xx (%)				
Missed Injection without OB (COVID-1 related)	xx (%)	xx (%)	xx (%)				
Missed Injection with OB (non-COVID-19 related)	xx (%)	xx (%)	xx (%)				
Missed Injection with OB (COVID-19 related)	xx (%)	xx (%)	xx (%)				
Late Out of Window Injections (days outside +7 day window)							
n	xxx	xxx	xxx	xxx	xxx	xxx	xxx
Mean	xxx.x	xxx.x	xxx.x	xxx.x	xxx.x	xxx.x	xxx.x
SD	xxx.xx	xxx.xx	xxx.xx	xxx.xx	xxx.xx	xxx.xx	xxx.xx
Median	xxx.x	xxx.x	xxx.x	xxx.x	xxx.x	xxx.x	xxx.x
Q1	xxx	xxx	xxx	xxx	xxx	xxx	xxx
Q3	xxx	xxx	xxx	xxx	xxx	xxx	xxx
Min	xxx	xxx	xxx	xxx	xxx	xxx	xxx

CONFIDENTIAL

213199

Timeliness of Injections Relative to Date of Projected Dosing Visits	Month 2	Month 4	Month 6	Month 8	Month 10	Month 12	Total
Max	xxx	xxx	xxx	xxx	xxx	xxx	xxx

CONFIDENTIAL

213199

Protocol: mid213199
Population: Safety

Page 1 of 1

Table SAF_T2

Summary of Adherence to CAB LA + RPV LA Dosing Schedule by Visit, Subgroup, and COVID Impacted/Non-Impacted (Intervention Phase)

Subgroup: xxxx {Programmer's Note: repeat for each subgroup}

COVID-19: xxx {Programmer's Note: repeat for non-impacted + impacted/non-impacted/impacted}

Timeliness of Injections Relative to Date of Projected Dosing Visits	Month 2	Month 4	Month 6	Month 8	Month 10	Month 12	Total
No. of Expected Injection Visits	xxxx	xxxx	xxxx	xxxx	xxxx	xxxx	xxxx
<-14 days	xx (%)	xx (%)	xx (%)				
-14 days to - 8 days	xx (%)	xx (%)	xx (%)				
-7 days to - 1 days	xx (%)	xx (%)	xx (%)				
0	xx (%)	xx (%)	xx (%)				

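### The late-injection block in shells SAF_T1 and SAF_T2 applies a +7-day limit at Month 2, where the protocol's Dose 2 window has no late allowance

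*SAP*

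**What the plan says.** Protocol 4.3.3 sets two windows. For Dose 2: "The dosing window for the second injections will be +0/-7 days from the projected target date (target date is established at Month 1". From Dose 3: "All subsequent injection windows (starting with Dose 3) will be +7/-7 days from the projected target date". Protocol 6.5.3 repeats the first without ambiguity: "The dosing window for Dose 2 allows administration -7days of the proposed visit date but not later". The schedule of activities reprinted in SAP 13.1.1 carries the same two windows.

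The text of SAP 13.5.2 follows the protocol: "Out of Window injections are determined based on criteria listed in protocol Section 4.3.3". It bins timeliness by actual minus projected date, and the injections covered by the "analysis are those after first injection at Month 1", so Dose 2 is the first one counted.

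The shells behind Tables 3.3 to 3.6 (SAP 13.12.7) are SAF_T1 and SAF_T2 in Appendix 13. Each has columns for Months 2, 4, 6, 8, 10 and 12 and for Total. Below the timeliness rows, which include "1 days to 7 days", is one block of summary statistics labelled "Late Out of Window Injections (days outside +7 day window". The label is the same for all columns.

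The share of injections given inside their window is a listed secondary endpoint (protocol section 3; SAP 2.2 and 8.1). Protocol 9.4.2 asks for it at Month 12 with 95% confidence intervals.

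**The concern.** The late block is the only part of either shell that uses the term out of window, and at Month 2 its limit is not the protocol's limit. A programmer cannot satisfy both the printed label and SAP 13.5.2 in that column, and the SAP does not say which prevails. The separate out-of-window categories that 13.5.2 lists appear in neither shell, so no other row puts the protocol rule into effect.

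Two things are at stake. One is a wrong count and wrong lateness values for Dose 2, the injection with the narrowest window. The other is the fidelity percentage. The shells have no row for it, so a reader must build it from the timeliness rows. A +7 label running across all columns invites adding -7 to +7 days everywhere, including Month 2.

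**Working it through.** There is no planned figure to reproduce. The check compares the two rules and then sizes the consequence.

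**Inputs.** Dose 2 upper limit +0 days and Dose 3 onward +7 days (protocol 4.3.3); label limit +7 days in all columns (shells SAF_T1 and SAF_T2); six assessed injections, Months 2 to 12 (shells); 450 patients (SAP 2.3), used only to size the effect.

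**Step 1: the late block at Month 2.** Let d be days after the target date.
- Protocol rule: Dose 2 is late for any d > 0, and days outside = d.
- Label as printed: late only for d > 7, and days outside = d - 7.

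| d (days late) | Protocol 4.3.3, days outside | Label as printed, days outside |
|---|---|---|
| 1 | 1 | not counted |
| 3 | 3 | not counted |
| 7 | 7 | not counted |
| 8 | 8 | 1 |
| 10 | 10 | 3 |
| 14 | 14 | 7 |

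So n is too small by the number of second injections 1 to 7 days late, and every remaining Dose 2 value is 7 days too low. Both errors pass into Total. The mean can move either way, because the omitted values are the small ones. With lateness of 3 and 10 days the correct mean is (3 + 10)/2 = 6.5, and the label gives 3 on n = 1. With 1, 1, 1 and 14 days the correct mean is 17/4 = 4.25, and the label gives 7 on n = 1.

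**Step 2: the timeliness rows.** These depend only on d, so their counts are unchanged. In the Month 2 column the row for 1 to 7 days late holds only out-of-window injections; in the columns from Month 4 it holds only in-window ones. In Total the two kinds are added together, so Total alone cannot yield the correct in-window percentage.

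**Step 3: size if -7 to +7 days is pooled in every column.** Let x be the percentage of second injections given 1 to 7 days late. With no dropout, expected visits = 450 × 6 = 2700, and Month 2 contributes 450/2700 = 16.7%. Overstatement = x points at Month 2 and x/6 points in the Month 12 Total. The documents do not give x; the values below are assumptions.

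| x (assumed) | Injections affected (450 × x) | Month 2, points | Total, points (x/6) |
|---|---|---|---|
| 2% | 9 | 2 | 0.33 |
| 5% | 22.5 | 5 | 0.83 |
| 10% | 45 | 10 | 1.67 |
| 20% | 90 | 20 | 3.33 |

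The ceiling for Total is 100/6 = 16.7 points. If out-of-window status is taken from SAP 13.5.2, the overstatement is 0.

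The divisor of 6 belongs to the Month 12 table with complete follow-up. Dropout raises Month 2's share. Table 3.3 is also an output of both interim analyses, which are timed to the third injection; a participant who has just reached Dose 3 has two assessed injections, so the figure there could approach x/2. At end of study the extension visits lower Month 2's share.

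**The case against.** The case for leaving this alone is a fair one. The SAP text already has the right definition, since 13.5.2 defers to protocol 4.3.3. The shells are examples and visibly lag the text: some efficacy shells carry a Q4W column header in a study dosed every two months, one disposition shell shows a program path from another study, and the adherence shells lack categories that 13.5.2 asks for. Second injections given 1 to 7 days late remain visible in their own row at Month 2, by country, site and subgroup. Listing 36 gives actual visit dates. On this view the label is a leftover.

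Much of that stands, and it rules out two stronger readings. A reader might infer that late second injections are shown as in window. They are not: the rows are bins of day differences, and no row in either shell is labelled in window. A reader might also infer that the fidelity result is overstated. The documents do not support that either: the shells do not compute the percentage, and overstatement needs someone to follow the label over 13.5.2 or to pool the rows at Month 2.

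What the objection does not remove is the conflict itself. These are the only adherence shells for a named secondary endpoint, and the one block that applies an out-of-window limit applies the wrong one at Month 2. Correct text elsewhere does not make the printed block correct.

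**Conclusion.** The inconsistency is real and is wrong as printed. In SAF_T1 and SAF_T2 the late block contradicts the Dose 2 window in protocol 4.3.3, which SAP 13.5.2 says governs. Followed literally, it drops second injections 1 to 7 days late and understates later ones by 7 days each, at Month 2 and in Total. That part needs no assumed rates. The timeliness counts are sound.

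Overstatement of the fidelity endpoint is a risk and has not been shown to occur. It is x points at Month 2 and about x/6 in the Month 12 Total if -7 to +7 days is pooled, and zero if 13.5.2 is followed. The size rests on an unknown x and on near-complete follow-up to Month 12. The correction is worth making because the endpoint has no explicit row and the edit is small. This is a point about reporting only, with no view on which dosing window is clinically appropriate.

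**What to change.** Reconcile SAF_T1 and SAF_T2 with SAP 13.5.2 and protocol 4.3.3:

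- Make the late block visit-specific, with days late counted from that visit's own protocol upper limit (+0 at Month 2, +7 from Month 4), and build Total from those values.
- Add a row for injections within the protocol window, n (%), by visit and in Total: -7 to 0 days at Month 2, -7 to +7 days from Month 4. Attach the 95% confidence interval that protocol 9.4.2 requires.
- Reconcile the timeliness categories. SAP 13.5.2 has a bin running from -7 to 1, which overlaps the bins for 0 and for 1 to 7 days; the shells end that bin at -1. This may be no more than a lost minus sign.

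The cost is an edit to two shells and the program behind Tables 3.3 to 3.6. No new data are needed. A percentage obtained by pooling -7 to +7 days in all columns would fall by the amount given in the working.
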